The most common adverse reactions ($\geq 10\%$) that occurred more commonly ($\geq 2\%$ over placebo) in enzalutamide-treated patients from the 2 phase 3, randomized, placebo-controlled clinical studies (CRPC2, MDV3100-03) were asthenia/fatigue, back pain, decreased appetite, constipation, arthralgia, diarrhea, hot flush, upper respiratory tract infection, peripheral edema, dyspnea, musculoskeletal pain, weight decreased, headache, hypertension, and dizziness/vertigo.

In clinical studies, seizure occurred in 0.5% of patients receiving enzalutamide. Because of the risk of seizure associated with enzalutamide use, patients should be advised of the risk of engaging in any activity where sudden loss of consciousness could cause serious harm to themselves or others. Enzalutamide should be permanently discontinued in patients who develop a seizure during treatment. Posterior reversible encephalopathy syndrome (PRES), a neurologic disorder that can present with rapidly evolving symptoms including seizure, headache, lethargy, confusion, blindness, and other visual and neurologic disturbances, with or without associated hypertension, has been reported in patients receiving enzalutamide in

the postmarketing setting. Enzalutamide should be permanently discontinued in patients who develop PRES during treatment.

Additional information on the clinical experience with enzalutamide is provided in the enzalutamide investigator brochure.

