In the phase 2 study 9785-CL-0222, which was also conducted in patients with chemotherapy-naïve metastatic CRPC, patients were randomized to enzalutamide or bicalutamide. A significant improvement in radiographic PFS was demonstrated in patients treated with enzalutamide versus bicalutamide with an observed hazard ratio of 0.60 (95% CI: 0.43, 0.83). In the phase 2 study MDV3100-09, patients with chemotherapy-naïve metastatic or nonmetastatic CRPC were randomized to enzalutamide or bicalutamide. A significant improvement in radiographic PFS was demonstrated in the overall population with an observed hazard ratio of 0.30 (95% CI: 0.21, 0.44) and in the nonmetastatic subgroup with an observed hazard ratio of 0.24 (95% CI: 0.10, 0.56).

In the 2 phase 3, randomized, placebo-controlled studies (CRPC2, MDV3100-03), the most common adverse reactions ($\geq 10\%$) that occurred more commonly ($\geq 2\%$ over placebo) in enzalutamide-treated patients were asthenia/fatigue, back pain, decreased appetite, constipation, arthralgia, diarrhea, hot flush, upper respiratory tract infection, peripheral

edema, dyspnea, musculoskeletal pain, weight decreased, headache, hypertension, and dizziness/vertigo. The important identified risks for enzalutamide, identified as important adverse events for which there is adequate evidence of a causal association with enzalutamide, include seizure, PRES, hypertension, fall, nonpathological fracture, neutrophil count decreased, and cognitive/memory impairment. Additionally, the important identified interactions associated with enzalutamide treatment include interactions with strong inhibitors or inducers of CYP2C8 and interactions with medicinal products that are substrates of CYP3A4, CYP2C9, or CYP2C19.

The totality of the efficacy and safety data suggests a positive benefit-risk assessment for the use of enzalutamide in men with CRPC, and for the continued investigation of enzalutamide in men with earlier stage prostate cancer.

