5.3. Permanent Treatment Discontinuation

Permanent treatment discontinuation is defined as cessation of study drug administration. Safety follow-up ([Section 5.4.1](#)) and long-term follow-up ([Section 5.4.2](#)) will still be performed.

Temporary treatment interruption due to an adverse event is not considered permanent discontinuation. Patients whose treatment is interrupted due to an adverse event and restarted will continue to have regularly scheduled study visits based on their randomization date.

The primary reasons for permanent treatment discontinuation are listed in [Table 5](#). Cross-references are provided to protocol sections with additional information.

Table 5. Primary Reasons for Permanent Treatment Discontinuation

Reason	Comment
Adverse event or intercurrent illness	Any intolerable adverse event that cannot be ameliorated by the use of adequate medical intervention or that in the opinion of the investigator or medical monitor would lead to undue risk if study treatment were continued. Refer to Section 8 .
Gross noncompliance with protocol (violation)	The medical monitor or investigator may request permanent discontinuation of study drug treatment in the event of a major protocol deviation, lack of cooperation, or noncompliance.
Disease progression	Study drug treatment will be discontinued after development of radiographic progression if the investigator considers continuing study drug not to be beneficial. Initiation of new therapy for prostate cancer (with the exception of cytotoxic chemotherapy, androgen receptor inhibitors, and investigational agents) at the time of radiographic progression will not mandate discontinuation of study drug if the investigator considers continuing study drug to be beneficial.
Laboratory abnormality defined by protocol	
Creatinine >354 µmol/L (4.0 mg/dL)	
AST, ALT, or total bilirubin >5 times the upper limit of normal (ULN) AST or ALT > 3 times ULN and total bilirubin > 2 times ULN without findings of cholestasis	
Absolute neutrophil count ≤750/µL	
Platelet count <50,000/µL	
Seizure	Regardless of resolution of any identified etiology. Refer to Section 1.4 .
Death	Refer to Section 1.1 .
Loss to follow-up	Refer to Section 5.5 .
Sponsor discontinuation of study	The sponsor reserves the right to terminate the study anytime as described in Section 13.6 . The sponsor will terminate this study following completion of the study objectives, or earlier if deemed necessary.

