Dose modification: Patients who experience a grade 3 or higher toxicity that cannot be ameliorated by the use of adequate medical intervention may interrupt treatment for 1 week or until the toxicity grade improves to grade 2 or lower severity. Subsequently, study drug dosing may be restarted at the original dose (160 mg/day) or a reduced dose (120 or 80 mg/day) in consultation with the medical monitor.

If enzalutamide is coadministered with a strong CYP2C8 inhibitor (ie, gemfibrozil), the dose of enzalutamide should be reduced to 80 mg once daily. If coadministration of the strong CYP2C8 inhibitor is discontinued, the enzalutamide dose should return to the dose used prior to initiation of the strong CYP2C8 inhibitor.

Patients whose treatment is interrupted due to an adverse event and restarted will continue to have regularly scheduled study visits based on their enrollment date in the open-label period. Patients will permanently discontinue treatment with enzalutamide for the following reasons:

- Adverse event: If intolerable and cannot be ameliorated by adequate medical intervention; or that in the opinion of the investigator or medical monitor will lead to undue risk if enzalutamide continues;
- Seizure or any condition that significantly predisposes the patient to seizure such as brain metastasis or clinically evident stroke;
- Initiation of cytotoxic chemotherapy or investigational therapy for prostate cancer;
- Persistent laboratory abnormality as follows:
 - Creatinine >354 $\mu\text{mol/L}$ (4.0 mg/dL);
 - Bilirubin, AST, or ALT >5-times the ULN;
 - AST or ALT > 3 times ULN and total bilirubin > 2 times ULN without findings of cholestasis;
 - Absolute neutrophil count $\leq 750/\mu\text{L}$;
 - Platelet count < 50,000/ μL .

Patients may also permanently discontinue enzalutamide treatment for the following reasons:

- Withdrawal of consent (patient decision anytime for any reason). Patients may withdraw consent for further treatment, but may still consent to participate in the long-term follow-up assessments of survival status and new prostate cancer therapies (via family, physician contacts, and public records). Study site personnel should document in the patient's source records the specific details of the procedures the patient allows (eg, long-term follow-up) or declines (eg, further treatment);

- Gross noncompliance with protocol procedures and/or study drug management;

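### Protocol Section 1.2 says to stop enzalutamide for PRES, but the open-label discontinuation list in Supplement 1, like Table 5, names seizure and not PRES

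*Protocol*

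**What the plan says.** **Background text.** Protocol Section 1.2 gives two parallel statements. For seizure: "Enzalutamide should be permanently discontinued in patients who develop a seizure during treatment". For PRES: "Enzalutamide should be permanently discontinued in patients who develop PRES during treatment". Neither depends on severity, tolerability or anyone's opinion. Section 1.4 names both among the important identified risks, which "include seizure, PRES, hypertension, fall, nonpathological fracture, neutrophil count decreased, and cognitive/memory impairment", but gives no discontinuation instruction.

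**Double-blind list.** Section 5.3 opens with "The primary reasons for permanent treatment discontinuation are listed in" Table 5. That table has a row for seizure, with the comment "Regardless of resolution of any identified etiology". It has no row for PRES. Its general adverse-event row covers "Any intolerable adverse event that cannot be ameliorated by the use of adequate medical intervention", and also events that the investigator or medical monitor thinks would lead to undue risk.

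**Open-label list.** The list in Supplement 1 is mandatory in form. One bullet reads "Seizure or any condition that significantly predisposes the patient to seizure such as brain metastasis or clinically evident stroke". Another is a general adverse-event bullet, built like the one in Table 5. PRES is not named.

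**Dose modification.** Section 6.2.4 and the matching paragraph of Supplement 1 let a patient with grade 3 or higher toxicity interrupt treatment and later restart, at full or reduced dose, in consultation with the medical monitor. Neither mentions PRES.

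**SAP.** Section 9.2 makes it a category of major deviation to meet a criterion for stopping study drug and not stop. Section 9.8.1.1 lists PRES as an adverse event of special interest.

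**The concern.** Two sentences with the same wording in Section 1.2 were treated differently when the discontinuation lists were written, and no text explains why. One became an explicit entry in both lists. The other stayed in the background section.

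This matters because the sponsor itself ranks PRES with seizure as an important identified risk. If the Section 1.2 sentence is a trial rule, the lists do not carry it. If it is only background, the protocol states an unconditional stop that it does not intend to enforce. An investigator with a PRES case that has no seizure would find an absolute statement in one place and a matter of judgment in the others. Two sites could handle or classify the same case differently and each point to the protocol. The open-label period includes former placebo patients who are starting enzalutamide for the first time.

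**Working it through.** No arithmetic applies beyond a count. The check compares each place where the documents name PRES with each place that governs stopping or restarting drug.

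**Where PRES is named.** Protocol abbreviation list, Section 1.2 and Section 1.4; SAP Section 9.8.1.1 and Appendix 2. Only Section 1.2 says anything about discontinuation.

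**What governs stopping and restarting.**

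| Text | Seizure named | PRES named | Route by which PRES could be reached |
|---|---|---|---|
| Protocol 1.2 | yes | yes | direct and unconditional |
| Table 5 (double-blind, concluded) | yes | no | seizure row if a seizure occurs; otherwise the adverse-event row |
| Supplement 1 list (open-label, ongoing) | yes | no | seizure bullet if a seizure occurs; otherwise the adverse-event bullet or, arguably, the predisposing-condition clause |
| Section 6.2.4 (double-blind dose modification) | no | no | general toxicity text; interruption and restart possible |
| Supplement 1 dose modification | no | no | general toxicity text; interruption and restart possible |

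Count over the two discontinuation lists: seizure in 2 of 2, PRES in 0 of 2.

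**Case A: PRES with seizure.** Section 1.2 describes PRES as a disorder that can present with seizure among other symptoms. If a seizure occurs, the seizure entry in either list applies outright and agrees with Section 1.2. There is no gap.

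**Case B: PRES without seizure.** Section 1.2 still applies as written. In Table 5 only the adverse-event row remains, and it depends on intolerability or opinion. In Supplement 1 there are two routes: the adverse-event bullet, with the same conditions, and the clause on conditions that significantly predispose to seizure. That clause is open-ended and could take in PRES, but its two examples are brain metastasis and stroke, and someone must judge that the predisposition is significant. The dose-modification paragraphs make no exception for PRES, so a reader who started from them could reach a restart that Section 1.2 does not foresee.

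**Cross-references.** The seizure row of Table 5 sends the reader to Section 1.4, but the discontinuation sentences stand in Section 1.2. The discontinuation text of Supplement 1 does not point to Section 1.2.

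**Consequence for the SAP.** The deviation category in SAP Section 9.2 needs a defined set of discontinuation criteria. If Section 1.2 counts, continuing after PRES is a major deviation. If only the lists count, Case B depends on judgment. The SAP does not say which text supplies the criteria.

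**The case against.** The strongest reply is that this is an omission and not a clash of rules. No text says a patient with PRES may continue. Table 5 presents itself as the "primary reasons for permanent treatment discontinuation", which does not claim to be exhaustive, and its adverse-event row can reach PRES through undue risk. The Supplement 1 list has an equivalent bullet and the open-ended predisposition clause. Restart is permissive and needs consultation with the medical monitor. Section 1.2 is part of the same protocol, and nothing suggests that general toxicity text overrides it. All of this stands, and it limits the point. It does not remove the point, because each of those routes without a seizure needs a judgment that Section 1.2 does not ask for.

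It can also be said that Section 1.2 is background and uses the word should. That is fair, and the force of the sentence is uncertain. But the seizure sentence has the same form and was made operative.

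Some stronger readings are tempting and not supported:

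- A reader might infer that two lists now in force lack the instruction. The synopsis says the double-blind period has concluded, so only Supplement 1 still governs treatment.
- A reader might infer that the open-label list leaves PRES to the general adverse-event bullet alone. The predisposition clause is a second, arguable route, and PRES with seizure is covered outright.
- A reader might infer that sites act on the lists and disregard Section 1. No text says so. Investigators also sign the protocol and acknowledge the investigator brochure, which is not available here.
- A reader might call PRES rare in this trial. The protocol says only that it has been reported after marketing.

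**Conclusion.** The inconsistency is real and narrow. It concerns PRES without seizure, and its practical weight lies in Supplement 1. For such a case the protocol states an unconditional stop in Section 1.2 and leaves the decision to judgment in the text that governs stopping and restarting. Whether continuing would breach a discontinuation criterion cannot be settled from the documents.

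The conclusion assumes that the Section 1.2 sentence was meant to apply to patients in this trial. If it was meant only to summarise experience elsewhere, the remedy is still to say so.

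No endpoint, error rate or estimate is touched, and PRES is collected and summarised as an event of special interest in any case. The SAP consequence has its own limit: Section 9.2 fixes the list of major deviations before unblinding and does not say how open-label cases are to be classified. The point is worth correcting because it concerns stopping drug for a risk the sponsor calls important, and the correction is small.

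**What to change.** The sponsor should reconcile Protocol Section 1.2, the discontinuation list and dose-modification paragraph of Supplement 1, Table 5 and Section 6.2.4, so that one consistent instruction on PRES stands in all of them. The Supplement 1 text comes first because it is still in use. The sponsor decides what that instruction is; this review does not say which rule is right.

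Two small repairs belong with it. The cross-reference in the seizure row of Table 5 should point to the section that holds the discontinuation sentences. SAP Section 9.2 should state which protocol text supplies the discontinuation criteria for the major-deviation category, and whether the category extends to the open-label period.

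The cost is a few lines of protocol text and one sentence in the SAP. No new data collection is needed and no planned efficacy analysis changes.

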1.2.1. Pharmacokinetics and Drug Metabolism

The current enzalutamide investigator brochure provides the most up to date information on enzalutamide PK and drug metabolism. In PK investigations in men with CRPC, enzalutamide was absorbed rapidly after oral administration, with the time to maximum plasma concentration (t_{max}) after a single dose typically occurring at 1 hour postdose. No major deviations from dose proportionality were observed over the dose range 30 mg to 600 mg. Due to the long terminal half-life (approximately 5.8 days), it took approximately 1 month to reach steady state. With daily oral administration, enzalutamide accumulation was observed at steady state with an 8.3-fold higher exposure (steady-state area under the curve, AUC) relative to a single dose. Based on the mean peak-to-trough ratio, the average difference between the peak (maximum plasma concentration, C_{max}) and trough (predose plasma concentration, C_{trough}) concentrations was $\leq 25\%$. As a result of the low daily fluctuations, plasma profiles at steady state resembled a constant infusion. The C_{trough} values in individual patients remained constant beyond day 28 of chronic therapy, suggesting time-linear PK once steady state was achieved. At steady state, plasma concentrations of enzalutamide and the active metabolite, N-desmethyl enzalutamide, were approximately the same.

In a drug-drug interaction study in male patients with CRPC (9785-CL-0007), a single oral dose of a substrate for cytochrome P450 (CYP) 2C8, CYP2C9, CYP2C19, or CYP3A4 was administered before and concomitantly with enzalutamide (after at least 55 days of dosing at 160 mg daily). Enzalutamide at steady state reduced the plasma exposure to midazolam (CYP3A4 substrate), warfarin (CYP2C9 substrate), and omeprazole (CYP2C19 substrate) by 86%, 56%, and 70%, respectively. Based on the magnitude of the decreases in exposure, enzalutamide is considered a strong inducer of CYP3A4 and a moderate inducer of CYP2C9 and CYP2C19 (Section 7.3). Substrates of CYP3A4, CYP2C9, and CYP2C19 with a narrow therapeutic index should be avoided if possible, as enzalutamide may decrease plasma exposure of these drugs. If enzalutamide is coadministered with warfarin (CYP2C9 substrate), additional international normalized ratio (INR) monitoring should be conducted. Enzalutamide did not cause clinically meaningful changes in exposure to pioglitazone (CYP2C8 substrate).

In a drug-drug interaction study in healthy male volunteers (9785-CL-0006), a single 160 mg oral dose of enzalutamide was administered alone or after multiple oral doses of gemfibrozil (strong CYP2C8 inhibitor). Gemfibrozil increased the composite area under the curve from time zero to infinity ($AUC_{0-\infty}$) of enzalutamide plus N-desmethyl enzalutamide by 2.2-fold with minimal effect on C_{max} ; therefore, strong CYP2C8 inhibitors should be avoided if possible as they can increase plasma exposure to enzalutamide plus N-desmethyl enzalutamide. If coadministration with a strong CYP2C8 inhibitor is necessary, the dose of enzalutamide should be reduced to 80 mg once daily. If coadministration of the strong

CYP2C8 inhibitor is discontinued, the enzalutamide dose should be returned to the dose used prior to initiation of the strong CYP2C8 inhibitor. The effects of CYP2C8 inducers on the PK of enzalutamide have not been evaluated in vivo ([Section 7.4](#)).

In the drug-drug interaction study in healthy male volunteers (9785-CL-0006), a single 160 mg oral dose of enzalutamide was administered alone or after multiple oral doses of itraconazole (strong CYP3A4 inhibitor). Itraconazole increased the composite $AUC_{0-\infty}$ of enzalutamide plus N-desmethyl enzalutamide by 1.3-fold with no effect on C_{max} . As this small change is not clinically meaningful, no starting dose adjustment is needed when coadministering enzalutamide with CYP3A4 inhibitors. The effects of CYP3A4 inducers on the PK of enzalutamide have not been evaluated in vivo ([Section 7.4](#)).

Additional information on the PK and drug metabolism of enzalutamide is provided in the enzalutamide investigator brochure.

1.3. Summary of Relevant Nonclinical Experience With Enzalutamide

The current enzalutamide investigator brochure provides the most up to date nonclinical information on enzalutamide. A complete assessment of toxicity has been conducted with enzalutamide, including evaluation of impurities. The toxicity program was designed to support treatment of men with CRPC and included acute (single-dose) and repeat-dose (up to 26 weeks duration in rats, 13 weeks in dogs) oral toxicity studies, genotoxicity studies, safety pharmacology studies, specific assessment of the effects on and recovery of the male reproductive system in dogs, and studies to determine the phototoxicity potential. The species included in the toxicity program were mice, rats, dogs, and cynomolgus monkeys. Toxicokinetic evaluations demonstrated that all of these species produce the 2 major human metabolites of enzalutamide, N-desmethyl enzalutamide and an inactive carboxylic acid derivative.

The toxicology studies tested enzalutamide formulated in Labrasol, the same excipient used in clinical studies and in the commercial product marketed for CRPC.

Long-term animal studies are being conducted to evaluate the carcinogenic potential of enzalutamide.

Enzalutamide did not induce mutations in the bacterial reverse mutation (Ames) assay and was not genotoxic in either the in vitro cytogenetic assay with mouse lymphoma thymidine kinase gene mutation or the in vivo mouse micronucleus assay.

Based on nonclinical findings in repeat-dose toxicology studies, which were consistent with the pharmacologic activity of enzalutamide, male fertility may be impaired by treatment with enzalutamide. In a 26-week study in rats, atrophy of the prostate and seminal vesicles was observed at ≥ 30 mg/kg/day (equal to the human exposure based on AUC). In 4-week and 13-week studies in dogs, hypospermatogenesis and atrophy of the prostate and epididymides were observed at ≥ 4 mg/kg/day (0.3 times the human exposure based on AUC).

Additional toxicology studies are ongoing and planned. Additional information on the nonclinical experience with enzalutamide is provided in the enzalutamide investigator brochure.

1.4. Enzalutamide Benefits and Risks Assessment

The current enzalutamide investigator brochure provides the most up to date information on the benefits and risks of enzalutamide treatment. As stated in [Section 1.2](#), more than 10,000 subjects and patients have been enrolled and treated worldwide in completed and ongoing clinical trials evaluating enzalutamide.

In the randomized, placebo-controlled phase 3 study CRPC2 (AFFIRM), the prespecified interim analysis at the time of 520 events demonstrated a statistically significant improvement in overall survival in patients with metastatic CRPC treated with enzalutamide versus placebo (hazard ratio = 0.631; 95% CI: 0.529, 0.752, $p < 0.0001$).⁹ The median survival was 18.4 months in the enzalutamide arm and 13.6 months in the placebo arm ($\Delta = 4.8$ months). The overall survival benefit was consistent across all subgroups, including age, baseline pain intensity, geographic region, and type of disease progression at entry. Enzalutamide treatment was superior to placebo for all secondary endpoints including the proportion of patients with a reduction in PSA level by 50% or more (54% vs 2%, $p < 0.001$), soft tissue response rate (29% vs 4%, $p < 0.001$), quality-of-life response rate (43% vs 18%, $p < 0.001$), time to PSA progression (8.3 vs 3.0 months; hazard ratio 0.25, $p < 0.001$), radiographic PFS (8.3 vs 2.9 months; hazard ratio 0.40, $p < 0.001$), and time to first skeletal-related event (16.7 vs 13.3 months; hazard ratio 0.69, $p < 0.001$). Based on the AFFIRM data, the US FDA approved enzalutamide in August 2012 for men with metastatic CRPC who previously received docetaxel therapy.

In the pivotal phase 3 study MDV3100-03 in patients with chemotherapy-naïve metastatic CRPC, the prespecified interim analysis at the time of 540 death events demonstrated statistically significant improvements in overall survival and radiographic PFS in patients treated with enzalutamide versus placebo. Data from this study resulted in a label extension for enzalutamide to include all patients with metastatic CRPC.

In the phase 2 study 9785-CL-0222, which was also conducted in patients with chemotherapy-naïve metastatic CRPC, patients were randomized to enzalutamide or bicalutamide. A significant improvement in radiographic PFS was demonstrated in patients treated with enzalutamide versus bicalutamide with an observed hazard ratio of 0.60 (95% CI: 0.43, 0.83). In the phase 2 study MDV3100-09, patients with chemotherapy-naïve metastatic or nonmetastatic CRPC were randomized to enzalutamide or bicalutamide. A significant improvement in radiographic PFS was demonstrated in the overall population with an observed hazard ratio of 0.30 (95% CI: 0.21, 0.44) and in the nonmetastatic subgroup with an observed hazard ratio of 0.24 (95% CI: 0.10, 0.56).

In the 2 phase 3, randomized, placebo-controlled studies (CRPC2, MDV3100-03), the most common adverse reactions ($\geq 10\%$) that occurred more commonly ($\geq 2\%$ over placebo) in enzalutamide-treated patients were asthenia/fatigue, back pain, decreased appetite, constipation, arthralgia, diarrhea, hot flush, upper respiratory tract infection, peripheral

edema, dyspnea, musculoskeletal pain, weight decreased, headache, hypertension, and dizziness/vertigo. The important identified risks for enzalutamide, identified as important adverse events for which there is adequate evidence of a causal association with enzalutamide, include seizure, PRES, hypertension, fall, nonpathological fracture, neutrophil count decreased, and cognitive/memory impairment. Additionally, the important identified interactions associated with enzalutamide treatment include interactions with strong inhibitors or inducers of CYP2C8 and interactions with medicinal products that are substrates of CYP3A4, CYP2C9, or CYP2C19.

The totality of the efficacy and safety data suggests a positive benefit-risk assessment for the use of enzalutamide in men with CRPC, and for the continued investigation of enzalutamide in men with earlier stage prostate cancer.

